Study recruitment occurs primarily in the hospital after the potentially eligible patients (those currently enrolled in the separate protocol AAAR7350 and interested in learning more about other research studies) have been admitted to the hospital and transferred to an inpatient bed. For some patients, study recruitment may occur post-discharge, up to 6 weeks following participants' presentation to the Emergency Department when they enrolled in the PHS study. Research coordinators for the present protocol will approach these patients, introduce the study and begin the informed consent process. Consenting participants are randomized to the intervention or control condition and complete baseline measures for the present protocol at the pre-training session (i.e., Time 1). Participants are given an electronic tablet device and a brief training on its use at the end of or within several days of this baseline session. For the subset of patients who provide signed consent and the brief tablet training for this intervention study in the hospital but who are then discharged prior to this session, the Time-1 session is conducted by phone while the patients are at home. An additional subset of patients who consent to participate in this study will come to CUMC after hospital discharge to conduct the questionnaires and the brief tablet training of the pre-training session (i.e., Time 1) in person. All participants then complete 8 sessions of the training (intervention or control version) at home twice per week for 4 weeks using the tablet. During this time their adherence to a heart medication is monitored using eCAP devices that they receive during enrollment or in the mail. For participants currently prescribed aspirin but no other heart medication, their adherence to aspirin will be monitored using the eCAP devices. For participants *not* currently prescribed aspirin but who *are* currently prescribed a heart medication other than aspirin, such as a non-aspirin antiplatelet, a beta-blocker, a statin, or an antihypertensive medication, their adherence to this other heart medication is monitored using the eCAP devices. Within several days following the completion of the 4-week training, participants are then contacted by phone for the post-training session (i.e., Time 2), during which they complete the same measures as completed at the Time-1 session. Then, participants return the tablet devices to CUMC researchers using pre-addressed envelopes/packages mailed to their homes. Finally, at 8 weeks after the Time-1 session, participants return the eCAP medication adherence monitoring devices to CUMC researchers also using pre-addressed envelopes/packages boxes.

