To measure FoR in ACS patients, and test its associations with ACS-induced PTSD, diminished future time perspective, and nonadherence to medications.

We will test the extent to which the hypothesized measures of the behavior change mechanisms in question (FoR, future time perspective) are intercorrelated in ACS patients with elevated acute stress symptoms. First, to test convergent validity, we will assess zero-order correlations among these measures. Specifically, we predict that—across both groups at Time 1 before the intervention—higher FoR will be associated with lower future time perspective (i.e., lower FTPS). Second, we will test whether higher FoR is associated with higher threat perception symptoms and overall lower proportion of days adherent to aspirin. Third, due to the within-subjects design, we will also assess test-retest reliability from Time 1 to 2, both across and within groups. In this way we will ensure that we have valid and reliable measures of our proposed mechanisms of behavior change.

Specific Aim 2.

To test whether a cognitive-affective intervention reduces FoR in ACS patients.

We will conduct a univariate ANOVA to assess the effect of the four-week intervention on pre-to-post change in FoR, the proposed target mechanism. Prior intervention research in cancer patients showed a small to moderate effect size of a cognitive-affective intervention on FoR symptoms (Hedge's g for difference in health worries from pre- to post-intervention = 0.35). In separate unadjusted tests with pre-to-post change in FoR (and in an exploratory test of future time perspective) as the outcome, we will enter group (intervention, control) as the predictor. We will repeat the tests adjusting for factors that may explain variance in health behavior, including demographic information (age, sex, race, ethnicity), medical severity assessed by GRACE risk score¹⁸ and Charlson comorbidity index,¹⁹ and depressive symptoms assessed by PHQ-8 score.²⁰

Specific Aim 3.

To test whether patients randomized to the intervention are more adherent to aspirin in the 2-month monitoring period within the first several months after their suspected ACS event, and secondarily, whether any intervention effect is explained by reduced FoR.

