In prior research with $N = 97$ at Time 1 using a similar intervention in cancer patients, a moderate effect size (Hedges $g = 0.54$) was found for differences in FoR between the intervention ($n = 64$) and control ($n = 36$) groups after 3 months and a somewhat smaller effect size (Hedge's $g = 0.35$) immediately after the 1-month intervention.¹³ Using G*Power 3.1,²² we tested a range of effect sizes for two levels of power. We determined that the present study is conservatively powered to change FoR in a fixed-effects one-way ANOVA with an effect size f of 0.35 or larger with a sample size of $N = 100$ (50 intervention, 50 control), given alpha = .05 and an intention-to-treat design in which missing data due to attrition are handled with multiple imputation.

4. Study Procedures

Patients will be considered for enrollment in the present study who are currently enrolled in AAAR7350 (the PHS study), who signed consent for AAAR7350 within the last 6 weeks (i.e., 42 days), who have indicated they are willing to hear about other research studies, and who have an Elevated Threat Perception score. Consent will be obtained using an IRB-approved consent form.

Pre-training/Time 1: For patients consenting to the study in the hospital, the pre-training session ideally occurs at this same visit. The RA will assess the potential mechanisms of behavior change verbally. At the end of this session, each patient will be given a tablet and an eCAP bottle with a brief explanation of their use. The estimated duration of this session is 45 minutes, including the consent process, questionnaires, and the brief training in the use of the tablet. A subset of patients will complete the consent process and receive the devices (eCAP bottle, tablet) with a brief training in the hospital and will then separately complete the questionnaires verbally by phone within several days. A separate subset of patients will complete the Time-1 session at CUMC sometime after hospital discharge but before 6 weeks (i.e., 42 days) have elapsed from the time of consent to the protocol AAAR7350.

Training phase: Random group assignment to the intervention or control group will be determined in a double-blind way by the programmed tasks on the tablet for each participant.

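### Aim 2 tests FoR change without adjusting for Time 1 FoR: a valid test, but usually less precise than a baseline-adjusted ANCOVA that needs no extra data

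*Combined protocol and SAP*

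**What the plan says.** All references are to the combined protocol and SAP.

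- **Section 3, Specific Aim 2, main test.** "We will conduct a univariate ANOVA to assess the effect of the four-week intervention on pre-to-post change in FoR, the proposed target mechanism". For the unadjusted tests, "we will enter group (intervention, control) as the predictor"; nothing else enters the model. Future time perspective is handled the same way as an exploratory outcome.
- **Section 3, Specific Aim 2, adjusted repeat.** "We will repeat the tests adjusting for factors that may explain variance in health behavior". The named factors are age, sex, race, ethnicity, GRACE score, Charlson index and PHQ-8. The list is introduced as examples, so it is not strictly closed, but Time 1 FoR is not on it.
- **Section 2, Study Design.** At the post-training contact participants are interviewed by phone, "during which they complete the same measures as completed at the Time-1 session". The baseline FoR score is therefore planned data.
- **Section 3, Specific Aim 1.** The correlation between the two time points is to be estimated in the trial: "we will also assess test-retest reliability from Time 1 to 2, both across and within groups". No value is assumed in advance.
- **Section 3, effect sizes.** Aim 2 cites from earlier work in cancer patients a Hedges "g for difference in health worries from pre- to post-intervention = 0.35". The power analysis refers to detecting change "in a fixed-effects one-way ANOVA with an effect size f of 0.35 or larger" with 50 patients per arm and alpha .05. It has no covariates and states no numerical power.

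**The concern.** The FoR score before training is usually the strongest single predictor of the score after training. Analysing the raw change subtracts the whole of the baseline score, which amounts to assuming that the regression of Time 2 on Time 1 has slope 1. If the true slope is lower, as ordinary regression to the mean implies, the subtraction over-corrects and adds noise to the group comparison. The covariates that are named are justified by their relation to health behaviour, whereas the Aim 2 outcome is FoR itself.

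Aim 2 asks whether the intervention moves its target mechanism. If the true effect is near the cited end-of-intervention value, 100 patients give limited power at moderate rho, and precision should not be given away. Because the covariate list is open-ended, baseline FoR could still be added later, but a choice made after results are seen would look post hoc.

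**Working it through.** **Inputs from the documents.** N = 100, 50 per arm (Study Design); alpha .05 and f = 0.35 (Power analysis); g = 0.35 immediately after the intervention (Aim 2 and Power analysis).

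**Assumptions.** The correlation rho between Time 1 and Time 2 FoR is not given and is varied over 0.3, 0.5, 0.7, 0.8 and 0.9. SDs at the two times are equal unless stated, the slope is common to both arms, and data are complete.

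**1. The plan's own design point.** For two equal groups the one-way ANOVA has noncentrality N f² = 100 × 0.35² = 12.25 with 1 and 98 df. Power is 93.4%. The smallest N for f = 0.35 is 68 for 80% power and 88 for 90%, so N = 100 is comfortable at that effect. With two equal groups d = 2f, so f = 0.35 is d = 0.70, whereas g = 0.35 is f = 0.175.

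**2. Variances.** Let s be the common SD.

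- Change score: s² + s² − 2 rho s² = 2(1 − rho)s².
- ANCOVA residual: (1 − rho²)s².
- Ratio, ANCOVA to change: (1 − rho²) / [2(1 − rho)] = (1 + rho)/2.

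At rho 0.5, for example, the two variances are 1.00s² and 0.75s², a ratio of 0.75. The planned test would then need 100/0.75 = 133 patients to match ANCOVA with 100. At rho 0.3, 0.7 and 0.9 it would need 154, 118 and 105.

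**3. Power at N = 100.** Noncentral F, with 98 denominator df for the change score and 97 for ANCOVA. If g = 0.35 is on the raw-score SD, f is 0.175/√[2(1 − rho)] for the change score and 0.175/√(1 − rho²) for ANCOVA. If the effect is on the change-score SD, the ANCOVA f is the stated f divided by √[(1 + rho)/2].

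| rho | Variance ratio | g = 0.35, raw SD: change v ANCOVA | g = 0.35, change SD: change v ANCOVA | f = 0.35, change SD: change v ANCOVA | Effect detectable with 80% power (raw SD): change v ANCOVA |
|---|---|---|---|---|---|
| 0.3 | 0.65 | 31 v 44% | 41.0 v 57.5% | 93.4 v 99.0% | 0.67 v 0.54 |
| 0.5 | 0.75 | 41 v 52% | 41.0 v 51.6% | 93.4 v 97.9% | 0.57 v 0.49 |
| 0.7 | 0.85 | 61 v 68% | 41.0 v 46.8% | 93.4 v 96.4% | 0.44 v 0.40 |
| 0.8 | 0.90 | 78 v 82% | 41.0 v 44.7% | 93.4 v 95.5% | 0.36 v 0.34 |
| 0.9 | 0.95 | 97 v 98% | 41.0 v 42.8% | 93.4 v 94.5% | 0.25 v 0.25 |

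Both scales are shown because the plan does not say which SD standardises g. On the raw-score SD, 80% power at g = 0.35 needs rho of about 0.79 with ANCOVA and 0.81 with the change score.

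**4. Unequal SDs.** With k = SD2/SD1, the ratio is k²(1 − rho²)/(1 + k² − 2 rho k). At rho 0.7 it is 0.63 for k = 0.8 and 0.98 for k = 1.25. At rho 0.8 and k = 1.25 it is 1.00, because the true slope rho × k is then exactly 1 and there is nothing to gain.

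**5. Where the lost variance comes from.** A chance baseline difference of 0.20 SD is one standard error at 50 per arm (√(2/50) = 0.20). It shifts the change-score estimate relative to ANCOVA by (1 − rho) × 0.20 SD: 0.10 at rho 0.5, 0.06 at 0.7 and 0.04 at 0.8. This is the same loss seen in a single trial, not an additional bias.

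**6. Validity by simulation.** With 8,000 trials per setting at N = 100 and no effect, rejection rates for change score and ANCOVA were 4.7% and 4.7% (rho 0.5), 5.1% and 4.8% (rho 0.7), and 4.6% and 4.6% (rho 0.9). With a true effect of 0.35, both methods averaged 0.35. The ratio of standard errors was about 0.87, 0.92 and 0.98, against 0.866, 0.922 and 0.975 from theory.

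**The case against.** The strongest reply is that nothing here is wrong. Change-score ANOVA is a legitimate, prespecified test that matches a question framed as change. At the protocol's own f = 0.35 it already has 93.4% power. The gap between f = 0.35 and g = 0.35 is a separate sample-size matter that ANCOVA does not cure. The gain depends on a correlation the documents do not give, and it may be close to nil.

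All of that stands, and it limits the point to one of efficiency. It does not remove the case for the change: apart from a negligible small-sample cost, the direction does not depend on rho, only the size does. Change can also stay as the outcome, because once Time 1 FoR is in the model, analysing change or Time 2 FoR gives the same group effect.

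Smaller objections also have some force:

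- Estimating the slope costs about 1% of variance at N = 100, so ANCOVA is very slightly worse in a narrow band around slope 1.
- PHQ-8 may recover part of the gain, but only in the adjusted repeat.
- Aim 2 ties the cited g to health worries, which is one subscale. Applying it to total FoR is an assumption.
- The Aim 3 mediator is also the unadjusted change, and the power statement describes a one-way ANOVA. Altering Aim 2 alone would leave those parts out of step.

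**Conclusion.** The point holds as a recommended improvement, not as a flaw that threatens the trial. The main Aim 2 test is valid but gives up precision whenever the slope of Time 2 on Time 1 FoR differs materially from 1. With equal SDs and complete data, adjusting for baseline cuts the variance of the group effect by 35% at rho 0.3, 25% at 0.5, 15% at 0.7 and 5% at 0.9.

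The benefit is worth having if the true effect is near g = 0.35 and rho is moderate: 7 to 13 points of power on the raw-score SD for rho from 0.7 down to 0.3. It is small at f = 0.35 or at rho of about 0.9, and absent if the slope happens to be 1. Confidence is high in the direction; the size rests on assumed values of rho and of the SD ratio.

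**What to change.** - Make the main Aim 2 model an ANCOVA: Time 2 FoR (or change in FoR) on group and Time 1 FoR.
- Treat future time perspective the same way, with its own Time 1 score.
- Add Time 1 FoR to the covariate-adjusted repeat and label that model a sensitivity analysis.
- Keep the unadjusted change ANOVA as descriptive.
- For consistency, use the same baseline adjustment in the group-to-mediator path of Aim 3 and Exploratory Aim 1, include Time 1 FoR in the multiple-imputation model, and reword the power statement so that it describes the main test.

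The core change is one sentence in the analysis plan and one degree of freedom; the consistency edits add a few more sentences. No patients, visits or measurements are added.

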We will test this mediational hypothesis using conditional process modeling with the PROCESS macro in SPSS.²¹ Although we will likely have insufficient power to test the question definitively, the results will inform whether a future larger trial is warranted. The behavioral outcome in the model is heart medication adherence from the eCAP data: mean proportion of adherent days in the 2-month monitoring period that occurs within several months after hospital discharge. The predictor is group (intervention, control). The mediator is pre-to-post change in FoR from Time 1 to 2. For a secondary analysis, we will test the outcome as the magnitude of the slope of change in weekly proportion of adherent days during the 2 months. We will evaluate whether there is a significant indirect effect that supports the notion that the intervention vs. the control training engaged the target mechanism in such a way that changes in the target predicted improved heart medication adherence over the month-long intervention.

Exploratory Aim 1.

We will test for off-target intervention effects on future time perspective, as well as the alternative mediation path through improvement in future time perspective.

The test will be structured as for Specific Aim 3 but with pre-to-post change in future time perspective as the tested mediator.

Exploratory Aim 2.

We will test whether the intervention is associated with greater increases in physical activity relative to the control group and whether this association is mediated by changes in FoR or future time perspective.

The test will be structured as for Specific Aim 3 and Exploratory Aim 1 but with physical activity as the tested behavioral outcome measure instead of medication adherence.

Power analysis.

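### The Aim 3 mediation model omits the covariates that the plan itself ties to health behavior, leaving the path from FoR change to adherence open to confounding

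*Combined protocol and SAP*

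**What the plan says.** All of this is in section 3, Statistical Procedures, of the combined protocol and SAP.

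**Specific Aim 2.** The group comparison is first run without covariates: "In separate unadjusted tests with pre-to-post change in FoR (and in an exploratory test of future time perspective) as the outcome". The plan then states: "We will repeat the tests adjusting for factors that may explain variance in health behavior, including demographic information". The list covers age, sex, race and ethnicity, "medical severity assessed by GRACE risk score" together with the Charlson index, and "depressive symptoms assessed by PHQ-8 score".

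**Specific Aim 3.** "We will test this mediational hypothesis using conditional process modeling with the PROCESS macro in SPSS". The model is then defined by three elements. "The behavioral outcome in the model is heart medication adherence from the eCAP data", summarized as the mean proportion of adherent days over two months; the predictor is randomized group; and "The mediator is pre-to-post change in FoR from Time 1 to 2". No covariate is named, either here or for the secondary analysis of the weekly adherence slope. A significant indirect effect is to be read as support for the training having acted on its target in a way that predicted better adherence.

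**Exploratory Aims 1 and 2.** Both take their structure from Aim 3, with a different mediator or a different behavioral outcome, so they too have no covariates.

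**The concern.** The stated reason for the covariates is that they may account for differences in health behavior. The two outcomes they are used for, change in FoR and change in future time perspective, are not behaviors, and in those tests randomization already protects the group comparison. The models that do have a behavior as outcome receive none of them.

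The gap falls where randomization gives no protection. Group is assigned; change in FoR is not. If more depressed or sicker patients both keep more of their fear and miss more doses, change in FoR will correlate with adherence without causing it. If the training also lowers FoR, the product of the two paths can look like mediation. Whether FoR is a modifiable mechanism is the central question in section 1, and the Aim 3 result is meant to inform the decision on a larger trial, so a false signal would have consequences.

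**Working it through.** The plan gives no figure for this point, so there is none to reproduce. The textual finding comes from setting Aims 2 and 3 side by side, as above. The arithmetic below only shows how large the effect could be.

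**Inputs**
- From the power analysis: N = 100, 50 per group, alpha 0.05. Effects on FoR: g = 0.35 just after the one-month intervention and g = 0.54 at three months (prior cancer study), and the powered effect f = 0.35, which with two equal groups is d = 2f = 0.70.
- Assumed, because the documents give nothing: one baseline confounder with correlation r with FoR change (less fall in fear) and −r with adherence, for r = 0.2, 0.3, 0.4. The true effect of FoR change on adherence is zero.

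**Step 1: bias of the mediator-outcome path.** Within groups, with standardized variables, the unadjusted coefficient is b = r × (−r) = −r². This gives −0.04, −0.09 and −0.16 SD.

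**Step 2: false rejection of that single path.** The expected test statistic is about r²√97 / √(1 − r⁴). For r = 0.3 this is 0.09 × 9.85 / 0.996 = 0.89, and P(|Z + 0.89| > 1.96) is about 14%. Simulation (6,000 trials per setting) gives 6.9%, 13.9% and 35.5% for r = 0.2, 0.3 and 0.4. With the confounder in the model the rate is 4.6% to 5.0%.

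**Step 3: chance that the group-to-FoR path is significant.** Noncentral F with 1 and 98 degrees of freedom and noncentrality f²N:
- no effect: 5%
- g = 0.35: f = 0.175, noncentrality 3.06, power 41.0%
- g = 0.54: f = 0.27, noncentrality 7.29, power 76.2%
- f = 0.35: noncentrality 12.25, power 93.4%

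**Step 4: the indirect effect, which is what Aim 3 tests.** Under a joint-significance rule both paths must be significant. The two tests are close to independent, so the false-positive rate is roughly step 2 × step 3. For g = 0.54 and r = 0.4: 0.762 × 35.5% = 27.1%. Direct simulation of the joint rule agrees to about one percentage point.

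| Effect of training on FoR | Product, r = 0.2 / 0.3 / 0.4 | Simulated, r = 0.2 / 0.3 / 0.4 |
|---|---|---|
| None | 0.3% / 0.7% / 1.8% | below 1% / 1% / 2% |
| g = 0.35 | 2.8% / 5.7% / 14.6% | 2.5% / 6% / 15% |
| g = 0.54 | 5.3% / 10.6% / 27.1% | 5% / 10% / 28% |
| d = 0.70 | 6.4% / 13.0% / 33.2% | 7% / 14% / 34% |

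With the confounder in both equations the simulated rate is at most about 6%. The joint rule is a stand-in for the PROCESS interval; a Monte Carlo interval gave similar values (4.7% / 12.3% at g = 0.35 and 13.7% / 32.4% at d = 0.70, for r = 0.3 / 0.4).

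**The case against.** Five counter-arguments deserve an answer.

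*Confounding alone does not produce mediation.* This stands. A reader might take the single-path rates of about 14% and 36% as the trial's rate of false mediation findings. The plan does not support that: its criterion is the indirect effect, whose first path is randomized. Without a training effect on FoR the rate stays near or below 2%. At g = 0.35, the prior that matches the timing of Time 2, r = 0.3 gives about 6%, hardly above nominal, although the adjusted rate there is only about 2% because the joint rule is conservative.

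*Size and direction are assumed.* This also stands. The mediator is a change score, so the confounder must predict change in FoR, not its level. Patients who start with high fear may fall further by regression to the mean; the correlation could then be near zero or reversed, and the bias would hide mediation. Adjustment removes the bias fully in the simulation only because there is a single confounder, measured without error.

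*The total effect is safe.* Correct. A reader might infer that the comparison of adherence between groups is confounded; it is randomized and is not.

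*Mediation is secondary and declared underpowered.* This limits the weight of the point but does not answer it. Low power concerns precision; confounding is bias.

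*The Aim 2 adjustment could be meant to carry over.* The text does not say so. It repeats the Aim 2 tests, and Aim 3 follows with a different model defined in full without covariates.

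**Conclusion.** The concern holds in a limited form. The plan names covariates for their link to health behavior, uses them for two outcomes that are not behaviors, and leaves them out of the mediation models that have one. The path from FoR change to adherence is therefore open to confounding by variables the plan already intends to use.

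How much this matters is unknown. Under the assumed correlations the harm is negligible if the training does not move FoR, small at r = 0.2 (at most about 7%), and material at r = 0.4 once the training works (15% at g = 0.35, 34% at d = 0.7). The exposure is thus greatest when the training succeeds on FoR, which is when a mechanism would be claimed. The documents do not show that depression or severity does confound this path, only that nothing in the model guards against it. This is a cheap improvement to a secondary analysis, not a flaw in the randomized comparisons.

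**What to change.** In section 3, Specific Aim 3, enter the Aim 2 covariates, using values measured at or before Time 1, in both the mediator equation and the outcome equation. Do the same for the mediation models of Exploratory Aims 1 and 2. Report adjusted and unadjusted results side by side, as Aim 2 already does, and base any statement that FoR is a mechanism on the adjusted result.

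Add two sentences. One should say when PHQ-8, GRACE and Charlson are obtained, since the Measures section describes none of them. The other should say that the indirect effect still assumes no unmeasured confounding of mediator and outcome.

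The cost is wording, provided the three scores are available from Time 1 or before; the documents do not confirm this. The statistical price is about 8 to 10 degrees of freedom out of 100 patients (one each for age, sex, ethnicity, GRACE, Charlson and PHQ-8, plus two to four for race, depending on its categories), in an analysis the plan already expects to be underpowered.

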Participants are asked to complete 8 at-home 30-minute intervention sessions (both CBM-A and CBM-I tasks are programmed to occur sequentially in one session). The schedule of sessions is 2 times per week. Participants will receive brief, automated text messages 2 times each week reminding them to complete these sessions. Phone calls will be conducted instead of text messages for participants without text message capability or for particular scheduled training sessions when participants do not respond to the text reminders.

Post-training/Time 2: A clinical coordinator will administer the measures by phone interview. Participants who prefer a home visit may complete the session in person and return their tablet to the interviewing clinical coordinator at that time. The estimated duration of this session is 45 minutes. All other participants will return their tablets and eCAP bottles via mail: one pre-addressed envelope/ package for the return of the tablet at 4 weeks after the Time-1 session and soon after completion of the Time-2 session and one separate pre-addressed envelope/package for the return of the eCAP bottle at 8 weeks after the Time-1 session.

Monetary compensation is administered via pay card in two installments. In the first installment of monetary compensation, participants receive \$20 at Time 1. Regarding the second installment of monetary compensation, it is structured such that participants are incentivized to return their devices with complete data. They receive \$5 for completing the 1st at-home tablet tasks session, \$5 for the 2nd, \$5 for the 3rd, \$5 for the 4th, \$10 for the 5th, \$10 for the 6th, \$20 for the 7th, and \$20 for the 8th tablet tasks session. They receive \$20 for completing the Time 2 interview. The second study compensation is contingent upon return of the tablet following Time 2. Finally, in the third study compensation, participants receive \$20 for returning the eCAP device. Thus, total study compensation for participants who complete all sessions is \$140 (\$20 in first installment + up to \$100 in second installment + \$20 in third installment).

References

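### Aim 3 does not carry the intention-to-treat and multiple-imputation commitment into its mediation model; run as written it is a complete-case analysis, and it is the only analysis given for the randomised adherence comparison

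*Combined protocol and SAP*

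**What the plan says.** All references are to the combined protocol and SAP.

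- **Missing data.** The only statement is in Section 3, Power analysis. The sentence that justifies 100 patients for the FoR ANOVA ends by describing "an intention-to-treat design in which missing data due to attrition are handled with multiple imputation".
- **Aim 3 method.** Section 3, Specific Aim 3: "We will test this mediational hypothesis using conditional process modeling with the PROCESS macro in SPSS". The predictor is group. On the mediator: "The mediator is pre-to-post change in FoR from Time 1 to 2". On the outcome: "The behavioral outcome in the model is heart medication adherence from the eCAP data: mean proportion of adherent days in the 2-month monitoring period". The paragraph names no analysis set, imputation step or pooling rule, and does not say what happens when the mediator or the outcome is missing.
- **Order of questions.** Aim 3 asks first whether the intervention arm is more adherent, "and secondarily, whether any intervention effect is explained by reduced FoR". No analysis of the first question is described apart from the mediation model.
- **Exploratory aims.** Exploratory Aims 1 and 2 take their structure from Aim 3, with a different mediator or behavioural outcome, and say nothing further on missing data.
- **How adherence data arrive.** Section 4, Post-training/Time 2, provides one mailing for the tablet at about 4 weeks and "one separate pre-addressed envelope/package for the return of the eCAP bottle at 8 weeks after the Time-1 session".

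**The concern.** The model needs two things that can go missing separately. Time 2 FoR depends on an interview at about 4 weeks. Adherence depends on a device posted back about a month later. A patient can give the interview and never return the device, or return the device after missing the interview. If the regressions are fitted to the collected file, anyone lacking either item drops out.

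Two things are at stake. The adherence comparison is a randomised comparison that does not need Time 2 FoR. Read off the mediation model, it loses patients for want of a variable it does not use. Separately, failing to return an adherence monitor is plausibly related to poor adherence, so the patients left may be the more adherent ones, and the arms need not lose patients equally. It is also unclear whether an unreturned device counts as attrition in the sense of the imputation sentence.

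**Working it through.** **The plan's own figure.** The sample-size statement concerns FoR, not adherence. With N = 100, f = 0.35 and alpha = 0.05, the noncentral F (lambda = 100 × 0.35² = 12.25; 1 and 98 df) gives power of 93.4%. The plan states no power level, so its claim is compatible with this figure but cannot be formally reproduced. Aim 3 has no power figure, and nothing in this calculation settles which patients Aim 3 uses.

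**Inputs.** From the documents: 100 patients, 50 per arm; the mediator needs Time 2; the outcome needs a returned eCAP. Assumed, because the documents give no rates: a proportion *a* without Time 2 FoR and a proportion *b* without a returned eCAP.

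**Patients available.**

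- Adherence comparison alone: 100(1 − b).
- Mediation model on complete cases: 100(1 − a)(1 − b) if the losses are independent; 100(1 − max(a, b)) if one group of losses lies inside the other; 100(1 − a − b) if they do not overlap.

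| a, b (assumed) | Adherence alone | Both: no overlap | Both: independent | Both: nested |
|---|---|---|---|---|
| 10%, 10% | 90 | 80 | 81 | 90 |
| 15%, 20% | 80 | 65 | 68 | 80 |
| 20%, 20% | 80 | 60 | 64 | 80 |
| 30%, 30% | 70 | 40 | 49 | 70 |

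For the 15%/20% row with independent losses, 100 × 0.85 × 0.80 = 68. Against the 80 patients with adherence data, the standard error is larger by a factor of √(80/68) = 1.08. Against 100 fully observed patients the factors are √(100/68) = 1.21 and √(100/80) = 1.12, but no analysis recovers 100 patients' worth of information. If the losses are nested, taking adherence from the mediation model costs no extra patients in these rows.

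**Bias from unreturned devices.** Let non-returners' true adherence be delta below that of returners, and let p be the non-return proportion in an arm. The arm's true mean is the returners' mean minus p × delta, so using returners alone overstates it by p × delta. The arm difference is then off by delta × (difference in p).

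- Equal non-return of 20%, delta 0.2 to 0.4: each arm is overstated by 0.04 to 0.08, and the difference is unbiased.
- Non-return of 15% and 25%, same delta: the difference is off by 0.10 × 0.2 = 0.02 to 0.10 × 0.4 = 0.04. The sign depends on which arm returns fewer devices.

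This bias arises because missingness depends on adherence that was not observed. Multiple imputation and full-information maximum likelihood both assume missing at random. They would remove it only as far as observed variables explain it.

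**The case against.** A reader might infer that the two paragraphs contradict each other, or that the named macro makes a completer analysis certain. The documents support neither. They do not describe how the macro treats incomplete records. Aim 3 is silent on missing data and does not adopt complete cases, and nothing prevents imputing first and fitting the model in each imputed file. The imputation clause also sits in the FoR power sentence: read narrowly, it promises nothing for Aim 3; read as a feature of the design, it covers Aim 3 and only the mechanics are absent. This stands against a charge of contradiction. It does not close the gap, because on the broad reading a pooling rule for the indirect effect is still needed, and on the narrow reading Aim 3 has no missing-data rule at all.

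Mitigations exist. Patients receive $20 and a pre-addressed package for returning the eCAP, and assignment is described as double-blind. Both arms receive feedback in training, contingent on the interpretation in the intervention arm only; whether that affects device return is speculation. These points reduce the risk of differential return without removing it.

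The plan also concedes: "Although we will likely have insufficient power to test the question definitively, the results will inform whether a future larger trial is warranted". That lowers the stakes of lost precision. It does not excuse avoidable bias, since the same sentence gives the result a role in deciding on a larger trial.

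**Conclusion.** The point holds as a gap that should be closed before analysis. The intention-to-treat and imputation commitment is not carried into Aim 3 or, by reference, the exploratory mediation aims. Executed literally on the collected file, the model is a complete-case analysis. The randomised adherence comparison, with no analysis of its own, would then also lose patients who returned an eCAP but lack Time 2 FoR.

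Any size is illustrative. Under assumed independent losses of 15% and 20%, adherence would be compared in 68 rather than 80 of 100 patients; the extra loss runs from none (nested) to 15 (no overlap). The 68 applies to adherence only if that effect is taken from the mediation model.

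A reader might also take the 0.02 to 0.04 bias as the price of using PROCESS. It is not: it rests on assumed non-return rates and on missingness tied to unobserved adherence, and standard imputation would be exposed to it too. It is the reason for a sensitivity analysis.

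**What to change.** Amend Section 3, Specific Aim 3, and apply the corresponding rules to Exploratory Aims 1 and 2:

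1. **Adherence comparison.** Test group on adherence separately from the mediation model, in all randomised patients, with multiple imputation. The imputation model should include group, baseline variables (including the covariates already listed under Aim 2) and whatever FoR data are available. State that an unreturned eCAP is missing data under this rule.
2. **Mediation.** Fit the mediator and outcome regressions within each imputed data set and pool, with an interval for the indirect effect that incorporates the imputation; or fit the path model by full-information maximum likelihood. PROCESS on complete cases may stay as a secondary run, with its number of patients reported.
3. **Sensitivity.** Add a delta-adjusted run in which imputed adherence for unreturned eCAPs is lowered over a stated range, for example 0.1 to 0.4, and report where the conclusion changes. Let delta differ by arm: with equal non-return, a common delta leaves the arm difference unchanged. With 20% non-return in each arm, deltas of 0.4 and 0.1 would move it by 0.20 × (0.4 − 0.1) = 0.06.

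The cost is SAP wording and modest extra programming in standard software. The delta values are assumptions and should be labelled so. Imputation will recover little for a missing outcome unless the observed variables predict adherence well; the more certain gain is from item 1, which keeps every patient with a returned eCAP in the adherence comparison.
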